mHealth-CR	Mobile health cardiac rehabilitation
MOP	Manual of Procedures
N	Number (typically refers to participants)
NIH	National Institutes of Health
OHRP	Office for Human Research Protections
OHSR	Office of Human Subjects Research
PCI	Percutaneous Coronary Intervention
PHQ-8	Patient Health Questionnaire (8 questions)
PI	Principal Investigator
QC	Quality Control
SAE	Serious Adverse Event/Serious Adverse Experience
SAQ-7	Seattle Angina Questionnaire (Short Version)
SF-12	12-Item Short Form Survey
SOP	Standard Operating Procedure
UBACC	University of California, San Diego Brief Assessment of Capacity to Consent
US	United States

CONFIDENTIAL

This material is the property of the NYU School of Medicine and Langone Medical Center. Do not disclose or use except as authorized in writing by the study sponsor

Protocol Summary

Title	REhabilitation at home uSIng mobilE health In older adults after hospitalizatioN for ischemic heart disease (RESILIENT)
Short Title	RESILIENT
Brief Summary	This study aims to evaluate whether mHealth-CR improves functional capacity in older adults (age ≥ 65) with IHD compared to usual care. Both groups will also receive a referral to (but not mandatory attendance of) traditional CR. A total of 400 eligible patients will be randomized in 3:1 manner to mHealth-CR versus usual care for assessment of primary endpoint. Enrollment will occur over approximately 42 months with an expected minimum of 3 months follow-up per participant.
Phase	Phase 3
Objectives	The study includes objectives related to both efficacy and engagement. The primary efficacy objective is to evaluate whether mHealth-CR improves functional capacity in older adults (age ≥ 65) with IHD compared with usual care alone. Secondary efficacy objectives are to evaluate whether mHealth improves: (1) goal attainment; (2) health status, (3) basic and instrumental activities of daily living, (4) hospital readmission, and (5) death in participants compared to usual care. The primary engagement objective is to characterize the engagement of participants with mHealth-CR and to elucidate barriers to participation.
Methodology	Open label, randomized clinical trial with blinded assessment of the primary endpoint.
Endpoint	Primary endpoint (efficacy) is functional capacity, measured by the change in 6 Minute Walk Distance (6MWD). Secondary endpoints (efficacy) are: (1) goal attainment, measured by goal attainment scoring (GAS); (2) change in reported health status, measured by SF-12 and SAQ-7; (3) changes in activities of daily living; (4) hospital readmission; and (5) death. Primary endpoint (engagement) is based on patterns of mHealth-CR use over study duration.
Study Duration	53 months (Month 7, Year 1 – Month 60, Year 5)
Participant Duration	3 months (from baseline visit to follow-up visit)
Duration of IP administration	42 months (throughout participant enrollment)
Population	Older adults (age ≥ 65) diagnosed with IHD within the New York, New Haven and Massachusetts metropolitan areas.
Study Sites	NYU Langone Health System, UMass Memorial Health Care (UMMHC), Bellevue Hospital, and Yale New Haven Health
Number of participants	400 participants expected to be enrolled across 2 sites.
Description of Study Devices	Devices provided to intervention arm only : portable tablet (Samsung Galaxy); activity tracking device (FitBit), blood pressure cuff (BodyTrace, Palo Alto, CA, Omron Kyoto, Japan), mHealth-CR software application (Moving Analytics, San Francisco, CA)
Reference Therapy	Usual care, which includes standard therapies post-AMI as deemed clinically appropriate. Both intervention and usual care arms will receive a referral to traditional ambulatory CR in accordance with best practice. However, attendance at ambulatory CR will not be facilitated or mandated by the study in the interest of a pragmatic trial.

[figure not shown]
CONFIDENTIAL

This material is the property of the NYU School of Medicine and Langone Medical Center. Do not disclose or use except as authorized in writing by the study sponsor

Statistical Analysis	
Primary endpoint (efficacy): Change in 6WMD will be assessed by calculating difference scores for each participant and comparing the intervention and usual care groups with an independent group t-test. Regression of 3-month 6MWD on a binary indicator of treatment group will also be measured, with adjustment for baseline 6MWD and the stratification factor (enrollment site).
 
Secondary endpoint (efficacy): Differences in secondary endpoints will be analyzed by the appropriate statistical test for continuous or categorical measures.
 
Primary endpoint (engagement): Measurements of engagement will use latent class analysis to identify profiles of engagement and assess trajectories.

----------------------	---

Schematic of Study Design

Flow Diagram

CONFIDENTIAL

This material is the property of the NYU School of Medicine and Langone Medical Center. Do not disclose or use except as authorized in writing by the study sponsor

1 Key Roles

[name], MPH – Principal Investigator

Leon H. Charney Division of Cardiology –NYU School of Medicine
[name]
[contact]

[name] – Sub-Investigator

Center for Cardiovascular Lifestyle Medicine – NYU Winthrop Hospital
[name]

[name] EdD, RCEP, MSN, AGNP-C – Sub-Investigator

Center for Cardiovascular Lifestyle Medicine – NYU Winthrop Hospital
[name]

[name] –Co-Investigator, Biostatistician

Department of Population Health – NYU School of Medicine
[name]
[contact]

[name] – Data Management, NYU DataCore

Department of Population Health – NYU School of Medicine
[name]
[contact]

[name], MS – Co-Investigator

Department of Geriatrics –NYU School of Medicine
[name]
[contact]

[name], EdD – Co-Investigator

Department of Population Health – NYU School of Medicine
[name]
[contact]

[name] – Co-Investigator

Leon H. Charney Division of Cardiology –NYU School of Medicine
[name]
[contact]

[name]—Yale Site Principal Investigator

Yale School of Medicine
[name]
[contact]

[name] –Yale Site Co-Investigator

Yale School of Medicine
[name]
[contact]

[name], MSHS –Consultant, Goal Attainment Scaling

University of Oklahoma Health Sciences Center
[name]
[contact]

CONFIDENTIAL

This material is the property of the NYU School of Medicine and Langone Medical Center. Do not disclose or use except as authorized in writing by the study sponsor

[name] – UMMHC Site Principal Investigator

University of Massachusetts School of Medicine

[name]

[contact]

2 Introduction, Background Information and Scientific Rationale

2.1 *Background Information and Relevant Literature*

Among older adults with ischemic heart disease (IHD), participation in ambulatory cardiac rehabilitation (CR) remains stubbornly low despite decades of evidence about its benefits; by recent estimates, fewer than two-thirds of eligible patients are referred, and even among those referred only half attend the first session.^{1–3} In addition to barriers faced by the general population (limited facilities, competing time demands, high out-of-pocket costs, prolonged wait time for space), older adults face additional particular barriers including lack of transportation, physical limitations, and cognitive impairments that make it especially difficult to use existing CR paradigms.^{4,5} Therefore, while older adults may have the greatest potential to benefit from CR because of their higher risk of adverse IHD-related sequelae, they are also the least likely to participate.^{4,6,7} In addition, it is unclear whether the usual goals set by ambulatory CR programs (e.g. risk factor modification, improvement in aerobic capacity) are aligned with older patients' goals, which often include outcomes such as independence and preservation of physical function.^{8,9}

Mobile health-enabled CR (mHealth-CR) for IHD, which involves delivery of rehabilitation via portable electronic devices, has proliferated rapidly in recent years.^{5,10,11} mHealth-CR programs are variable but typically include exercise documentation, hemodynamic assessment, video education, and electronic communication with an exercise therapist; these may be stand-alone components or an adjunct to traditional ambulatory CR programs.^{5,11} Professional guidelines recommend that CR be technically innovative and patient-centered,²² and mHealth-CR provides a novel opportunity to meet these goals; mHealth-CR involves mobile device-based software for patients to document exercise, control risk factors (e.g., blood pressure [BP]), access education materials, review physical activity, and communicate electronically with clinicians. mHealth-CR, used as a standalone intervention or as an adjunct to traditional CR,^{5,10} promises to promote physical activity and self-care skills, and to allow outreach to those who cannot access traditional CR due to geographical or financial barriers.²³

2.2 *Rationale*

While mHealth-CR has the potential to increase engagement by reducing participation barriers, it remains largely untested outside of small studies in relatively young, healthy persons. It is therefore unclear what proportion of older adults with IHD and barriers to traditional CR (who may benefit the most) are able to engage with mHealth-CR, and whether mHealth-CR in addition to usual care leads to better outcomes than usual care in this population. Further, to our knowledge, mHealth-CR has never been individualized to align with the unique functional limitations and goals of older adults with IHD.

We therefore propose to conduct a clinical trial within two academic health systems to evaluate mHealth-CR in patients age ≥ 65 years. In this trial embedded within the current standard of care, patients in both arms will receive a standardized referral to traditional ambulatory CR at hospital discharge, in accordance with professional guidelines² (typically started within 4 weeks at our institutions). Intervention arm participants will also receive mHealth-CR, initiated immediately, for 3 months.

CONFIDENTIAL

This material is the property of the NYU School of Medicine and Langone Medical Center. Do not disclose or use except as authorized in writing by the study sponsor

Our central hypotheses related to efficacy are that mHealth-CR will (1) improve functional capacity (primary outcome), (2) improve goal attainment, health status, and activities of daily living, and (3) lower rates of hospital readmission and death (secondary outcomes). We expect the benefits of mHealth-CR to mirror those of traditional ambulatory CR on cardiorespiratory fitness and risk factor modification, which is grounded in behavior change theory.^{30,31} Implementation of mHealth-CR has the potential to engage patients earlier than traditional CR, and with more frequent interaction, while simultaneously reducing barriers such as transportation and cost.

Our central hypothesis related to engagement is that we will identify distinct trajectories of engagement and characteristics that predict membership in each category. By design, we will only approach patients over age 65. While we expect that mHealth-CR will increase access, residual barriers are likely. Our hypothesis is driven by the Technology Acceptance Model v.3 (TAM3),³² based on the Theory of Reasoned Action, which asserts that perceptions of usefulness and ease of use influence adoption of a new technology. As with other technologies, selected subgroups are likely to have distinct engagement patterns,³³⁻³⁵ although these characteristics with mHealth-CR are as yet undefined. Our study therefore provides necessary foundational work needed to understand which patients may be optimal candidates for future mHealth interventions.

mHealth-CR represents an innovative approach to behavior change that takes advantage of mobile devices and combines remote monitoring technology with personalized feedback to improve patient care. This intervention has the potential to overcome existing barriers to CR utilization by engaging patients in their daily lives to promote physical activity and other healthy lifestyle behaviors. Because older adults may experience challenges with the technology, our design couples mHealth-CR with personal contact by an exercise therapist; we believe this hybrid approach may be particularly successful in engaging older adults.

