10.4.2 Analysis of the Primary Efficacy Endpoint(s)

6MWD

We will assess the difference in 6MWD by calculating difference scores for each participant and comparing the intervention and usual care groups with an independent group t-tests allowing for unequal variances. We will also regress 3-month 6MWD on a binary indicator of treatment group, with adjustment for baseline 6MWD and the stratification factor (enrollment site). While randomization should obviate the need for additional adjustment, we will explore whether adjustment for participant-level characteristics (e.g., demographic factors or referral to ambulatory CR) is necessary, using the change-in-estimate criterion. We realize that engagement with the mHealth-CR program may also affect attendance and engagement with structured ambulatory CR programs. We intend to explore this as a mediator of the effect of assignment to the intervention arm. We will use structural equation models to estimate the direct and indirect effects of mHealth, where the direct effect is that of mHealth-CR on the 6MWD, and the indirect effect is mediated through attendance at structured ambulatory CR.

Engagement

We hypothesize that (1) among participants offered mHealth-CR, there will be distinct trajectories of engagement (e.g., sustained engagement, disengagement, reengagement, deteriorating engagement); and (2) there will be significant differences in participant characteristics among these groups. While our aim is largely exploratory (given the paucity of data on mHealth-CR engagement), we will test whether the following characteristics are significant: age (≥ 80 years), sex, race/ethnicity, comorbidity burden (≥ 2 chronic medical conditions), frailty, social support (based on living alone), cognitive impairment (based on Mini-Cog), and depressive symptoms (based on PHQ-8). We selected these factors based on literature related to engagement in other technologies. We will conduct latent class analysis to identify profiles of engagement and explore whether these factors indicate membership in a class; these models use maximum likelihood estimation,

CONFIDENTIAL

This material is the property of the NYU School of Medicine and Langone Medical Center. Do not disclose or use except as authorized in writing by the study sponsor

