Health status at 3 months will be assessed using linear regression with adjustment for baseline levels and a binary treatment indicator; if necessary, health status scores will be log-transformed to improve the approximation to normality. Activities of daily living (BADLs and IADLs) will be assessed using longitudinal models for interval scores, with indicators to incorporate time, a binary indicator of treatment group, and patient-level random effects to accommodate repeated assessments within individuals; if interval scores are not approximately normally distributed, suitable transformations will be sought. Hospital readmission and death will be evaluated using Kaplan-Meier estimates and tested with logrank statistics, as well as investigated using Cox proportional hazard models with adjustment for confounders if necessary. As with the models for the primary outcome, in each model described we will assess the need for adjustment for confounders using the change-in-estimate criterion.

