10.5 Sample Size

We will randomize 400 participants using a 3:1 allocation, resulting in 300 participants in the intervention group and 100 participants in the usual care group. While we will aim to minimize participant dropout, we include adjustment for up to 20% dropout in each arm, resulting in about 320 participants with evaluable endpoints (240 intervention, 80 usual care). We wish to be able to detect a clinically meaningful difference between groups in our primary efficacy endpoint, change in 6MWD from baseline to 3 months. A recent meta-analysis⁵⁷ found an average difference in 6MWD of about 60 meters before and after traditional CR. Perera et al. determined this degree of change in 6MWD to be clinically meaningful based on its relationship to other health status measures.⁹⁸ Minneboo et al., however, also estimated an improvement in 6MWD in a control group of approximately 35 meters.⁵⁹ We therefore require adequate power to detect a difference between groups of less than 25 meters in change in 6MWD (i.e., the difference between a 60-meter improvement in the intervention group and a 35-meter improvement in the usual care group); this is the same amount estimated by Gremeaux et al. as a minimal clinically important difference in patients with IHD.⁹⁹ Assuming a conservative standard deviation estimate of 60 meters,⁵⁷ 320 participants provide approximately 90% power to detect a difference between groups of 25 meters, using a two-sided, 0.05-level test; there is 80% power to detect a difference

CONFIDENTIAL

This material is the property of the NYU School of Medicine and Langone Medical Center. Do not disclose or use except as authorized in writing by the study sponsor

between groups as small as 22 meters. This sample size also provides at least 80% power to detect reasonable effect sizes in secondary endpoints.

While the sample size was determined to provide sufficient power to detect a clinically meaningful difference in the primary outcome of 6MWD, it enables comparisons of secondary efficacy endpoints as well. The table below shows clinically meaningful effect sizes for these outcomes, and gives the power to detect these effect sizes

CONFIDENTIAL

This material is the property of the NYU School of Medicine and Langone Medical Center. Do not disclose or use except as authorized in writing by the study sponsor

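### Section 10.4.2 allows unequal variances in the change-score t-test but names no standard error for the adjusted 6MWD regression; under 3:1 allocation the ordinary one is miscalibrated if residual spread differs by arm

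*Combined protocol and SAP*

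**What the plan says.** Section 10.4.2 gives two analyses of the primary efficacy endpoint. The first forms a change score for each participant, "comparing the intervention and usual care groups with an independent group t-tests allowing for unequal variances". The second is introduced as an addition: "We will also regress 3-month 6MWD on a binary indicator of treatment group", adjusting for baseline 6MWD and enrollment site. No variance estimator is named for the second.

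The Protocol Summary repeats both. Its regression sentence reads "Regression of 3-month 6MWD on a binary indicator of treatment group will also be measured, with adjustment for baseline 6MWD and the stratification factor", again with no variance estimator, and its t-test appears without the unequal-variance wording.

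Section 10.4.3 uses the same kind of model for a secondary endpoint: "Health status at 3 months will be assessed using linear regression with adjustment for baseline levels and a binary treatment indicator". It too names no standard error.

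Section 10.5 sets the allocation: "We will randomize 400 participants using a 3:1 allocation, resulting in 300 participants in the intervention group and 100 participants in the usual care group". After 20% dropout per arm it expects about 240 and 80 evaluable participants. Power rests on one SD for both arms: "Assuming a conservative standard deviation estimate of 60 meters".

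**The concern.** The plan guards against unequal spread in one of its two analyses of the primary endpoint and is silent in the other. Under 1:1 allocation this would hardly matter, because the pooled and unequal-variance standard errors coincide. Under 3:1 they do not. Ordinary least squares pools the residual variance, so the large arm dominates it, whereas the actual variance of the treatment coefficient depends mainly on the small arm.

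At stake are the calibration of the adjusted p-value and interval, and agreement between the two analyses. With different variance assumptions they could fall on opposite sides of 0.05 for a purely technical reason. Leaving the estimator open also allows it to be chosen after the data are seen.

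**Working it through.** **Inputs.** From Section 10.5: 240 intervention and 80 usual-care evaluable, SD 60 m, difference 25 m, two-sided 0.05. Arm-specific SDs are assumptions. What matters for the regression is the residual SD after adjustment for baseline and site, and the documents give no value by arm. Type I error depends only on the ratio of the two SDs; power depends on their level as well.

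**The plan's own figures.** SE = 60 × √(1/240 + 1/80) = 7.75 m.
- Power at 25 m = Φ(25/7.75 − 1.96) = 89.8%, against a stated 90% or so.
- Power at 22 m = Φ(22/7.75 − 1.96) = 81.1%, against a stated 80%.

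Both reproduce.

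**Ordinary versus actual standard error.** Let s1 and s0 be the intervention and usual-care SDs.
- Actual variance of the effect: s1²/240 + s0²/80.
- Ordinary (pooled) variance: [(239·s1² + 79·s0²)/318] × (1/240 + 1/80), which is very nearly s1²/80 + s0²/240. Each arm's variance is in effect divided by the other arm's sample size.
- Type I error = 2 × [1 − Φ(1.96 × ordinary SE / actual SE)].

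**Worked case, intervention 75 m and usual care 60 m.**
- Ordinary: 75²/80 + 60²/240 = 70.31 + 15.00 = 85.31, SE 9.24 m.
- Actual: 75²/240 + 60²/80 = 23.44 + 45.00 = 68.44, SE 8.27 m.
- Ratio 1.117, critical value 1.96 × 1.117 = 2.19, type I error 2.9%.
- Power at 25 m with the ordinary SE: Φ(25/8.27 − 2.19), about 80%.
- Power at 25 m with a correct SE: Φ(25/8.27 − 1.96), about 86%.

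**All cases.** The last two columns come from simulating the regression itself (baseline, four sites, normal residuals, 20,000 runs per scenario).

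| SD intervention / usual care (m) | Ordinary SE (m) | Actual SE (m) | Type I error | 95% CI coverage | Simulated, ordinary | Simulated, HC3 |
|---|---|---|---|---|---|---|
| 60 / 60 | 7.75 | 7.75 | 5.0% | 95.0% | 5.1% | 5.0% |
| 66 / 60 | 8.33 | 7.95 | 4.0% | 96.0% | not run | not run |
| 60 / 66 | 7.95 | 8.33 | 6.2% | 93.8% | not run | not run |
| 75 / 60 | 9.24 | 8.27 | 2.9% | 97.1% | 3.0% | 4.8% |
| 60 / 75 | 8.27 | 9.24 | 7.9% | 92.1% | 8.0% | 5.1% |
| 90 / 60 | 10.79 | 8.87 | 1.7% | 98.3% | 1.8% | 4.7% |
| 60 / 90 | 8.87 | 10.78 | 10.7% | 89.3% | 10.9% | 5.1% |

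HC2 gave 5.0% to 5.4% in the simulated scenarios. With equal SDs, a simulation of 6,000 trials put power at 89.8% with the ordinary standard error and 89.1% with HC3.

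**The case against.** A reader might infer that the plan relies on an equal-variance standard error and is therefore wrong as written. The documents do not support that: they name no estimator, and the ordinary one is only what a regression described without further detail would usually get. The gap is an unspecified choice.

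A reader might also infer that the primary result is at risk. The analysis listed first is the t-test, which already allows unequal variances, and the power statement reproduces as a plain two-sample comparison. The regression is an addition. Which of the two governs is not stated, but that is a separate question that a robust standard error would not settle.

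It would likewise be wrong to lead with the inflated error rates. The plan's reasons to expect unequal spread are the individualised exercise programme (6.1.1, 6.1.2, 7.1.1) and the distinct engagement trajectories hypothesised among those offered mHealth-CR (2.2, 10.2). Both would widen the larger, intervention arm, which is the conservative direction. Nothing comparable points to a more variable usual-care arm. At a 10% SD difference the error is small either way.

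Finally, Section 10.4.1 promises to examine distributions when choosing tests, and Section 10.4.3 says the secondary analyses follow the primary ones. The latter can fairly be read as carrying the unequal-variance t-test over to the comparison of goal-attainment T-scores. Neither statement fixes a standard error for a regression.

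These objections limit the size and certainty of the point. They do not remove the gap.

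**Conclusion.** The point holds as a modest, inexpensive improvement. The adjusted regression has no stated standard error, and the ordinary one would be miscalibrated under 3:1 allocation if residual spread differs by arm. The likelier consequence is a loss of about 6 points of power at 25 m when the intervention SD is 75 m and the usual-care SD 60 m. The less likely one is a type I error of about 7.9% with those SDs reversed. Both figures rest on assumed SDs, on 240 versus 80 evaluable participants, and on the ordinary standard error actually being used. The health-status regression has the same gap, and the type I error figures carry over to it for the same SD ratio and sample sizes.

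**What to change.** In Section 10.4.2 and the Protocol Summary, state that the standard error, confidence interval and p-value for the treatment coefficient come from a heteroscedasticity-consistent estimator, for example HC3, in keeping with the unequal-variance t-test. HC2 or arm-specific residual variances would also serve; what matters is that one is named in advance. Apply the same rule to the health-status regression in Section 10.4.3. Adding the unequal-variance wording to the t-test in the Protocol Summary is only an alignment with 10.4.2.

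The cost is a sentence in each place and one software option, with no change to data collection. If the variances are in fact equal, the loss is under 1 point of power.
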